- Evaluate the effects of each behavior change technique message (i.e., BCT message) on daily adherence to weight loss behaviors in a 6-month micro-randomized trial among young adults.
- Determine whether the effects of BCT messages on proximal outcomes change over time.
- Assess whether the effects of BCT messages on proximal outcomes are moderated by participants’ contextual factors.

Test Article(s)
(If Applicable)

All participants will receive a core 6-month weight loss intervention that includes evidence-based lessons, behavioral skills training, and daily self-monitoring of weight, dietary intake, and physical activity.

Study Design

The Nudge trial applies the Multiphase Optimization Strategy (MOST) framework and uses a microrandomized trial design to test the effects of 7 types of behavior change technique (BCT) messages on achievement of daily weight-related goals among 201 young adults. All participants will receive a 6-month behavioral weight loss intervention using our Nudge mobile app, which includes evidence-based weekly lessons, tailored feedback, self-monitoring, and daily BCT messages. Participants will receive a wireless scale, activity tracker, and track “red” foods (high-calorie foods) in the app and have 3 goals: weigh daily, a daily active minutes goal that gradually increases if met, and a daily red foods limit. At 3 decision points per day, participants will be microrandomized to receive or not receive 1 of 7 types of BCT messages. The outcome to be tested is the effect of BCT messages on achievement of same-day goal achievement (weighing, active minutes goal, red food limit). Assessments of the primary outcomes will occur daily, with assessments of secondary outcomes at 0, 3 and 6 months.

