3. STUDY PROCEDURES

Data Collection

Measures of the primary outcomes (daily weighing and achievement of active minutes goal and red food limit) will be collected daily throughout the study via self-monitoring tools (described below). All study participants will complete objective weight measurements and self-administered online surveys at baseline, 3 months, and 6 months post-intervention. Participants will also complete two dietary recalls at baseline and two dietary recalls at 6 months to measure average dietary intake. Participants will receive \$50, \$25, and \$75 for completing baseline, 3, and 6-month assessments, respectively. Online surveys will include measures of theoretical mediators, other psychosocial constructs, and process measures. We will send emails and texts prompting participants to complete assessments, with follow-up emails and phone calls to non-respondents, as necessary. Measures and timing are described below.

Measures

Primary Proximal Outcome Measures (collected daily)

Intervention messages are intended to promote achievement of 3 daily weight-related behavioral goals: weigh daily, meet a daily active minutes (AM) goal, and stay at or under a daily RF limit. Thus, the primary outcome is the achievement of behavioral goals on the day of randomization (i.e., until 12:00AM).

Met daily weighing goal. Weighing behavior will be objectively measured daily using a smart scale (Fitbit Aria Air, San Francisco, CA) at the participant's home. Participants will be instructed to weigh themselves daily on the scale in light clothing and without shoes. A dichotomous indicator of whether the participant weighed will be calculated.

Met daily active minutes (AM) goal. Participants will have a daily AM goal that may change or stay the same at the beginning of each program week. Fitbit trackers will be used to collect daily AM data, defined by

Fitbit as physical activity of at least moderate-to-vigorous intensity that is accumulated in 10-minute bouts. We will calculate a dichotomous outcome of whether a participant met their daily AM goal (days with no tracker wear are counted as not meeting the goal) on the day of randomization.

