Stayed at or under red foods (RF) limit. Participants will have a daily RF limit that is determined by their sex and baseline weight. Daily RF intake will be calculated from participants' recorded RF in the study app. We will calculate a dichotomous outcome of whether a participant stayed at or under their RF limit (days without complete tracking [defined as tracked RF consumed during dinner plus breakfast or lunch, or if they reached or exceeded their RF limit], are counted as not meeting the RF limit).

Secondary Outcome Measures

Weight will be measured at baseline, 3 months, and 6 months at home using the smart scale. Participants will be asked to weigh themselves three times in a row, upon waking and before eating, in light clothing, without shoes, and the three weights will be averaged and used to calculate absolute weight change and percent weight change over time.

Proportion of days met daily weighing goal will be calculated as the percentage of study days (out of 168) a participant weighed. *Proportion of daily AM goal met* will be calculated as the proportion of daily AM goal met each day of the study using activity tracker data. *Proportion of daily RF limit* will be calculated as the percentage of the daily RF limit recorded each day of the study in the study app. The *total number of AM* and the *total number of RF* on the day of message randomization will be measured for each day of the study. Following the day of message randomization, we will measure *met daily weighing goal tomorrow*, *met daily AM goal tomorrow*, and *stayed at or under daily RF limit tomorrow*.

Tertiary / Exploratory Measures

Behavioral measures

- *Self-reported dietary intake* will be assessed using the NCI's Automated Self-Administered 24-hour Recall (ASA-24; National Cancer Institute) at baseline and 6 months. Participants will complete two unannounced self-reported recalls; one weekday and one weekend day.
- *Self-reported physical activity* at baseline, 3, and 6 months will be assessed with the Paffenbarger Physical Activity Questionnaire (PAQ) which assesses leisure-time activity and provides an estimate of minutes per week of moderate-to-vigorous intensity, and calories/week of light (5 kcal/min), medium (7.5 kcal/min), and high (10 kcal/min) intensity activities (Paffenbarger et al., 1978).

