We will test: 1) whether any intervention message (versus no message) increases adherence to daily weight loss behaviors among young adults, 2) whether a behavior-specific message (versus not receiving the behavior-specific message) increases adherence to the respective behavioral goal, and 3) finally the unique effect of each BCT message for the three proximal outcomes. We will use generalized estimating equations (GEE) with an independence working residual correlation matrix to account for nesting of observations within individuals.⁵⁸ and use Benjamini-Hochberg-Storey correction for multiple testing.⁵⁹

Analysis of whether effects of BCT messages change over time

We will also examine whether the effects of BCT messages on daily adherence to weight loss behaviors change over time (week in program, time of day) and, if so, the nature of the change (e.g., when effects disappear). Thus, we will expand upon the model described above by: 1) including linear and quadratic main effects of time and interaction terms, between an indicator of day in the program and treatment assignment, to test whether the treatment effect changes over time.⁵⁸ We will examine differences in the average and estimated time trends in treatment effects of receiving a behavior-specific message, and then the unique effect of each BCT message for the three proximal outcomes.

Analysis of whether effects of BCT messages are moderated by participants' contextual factors

We will evaluate whether the causal effect of receiving a BCT message interacts with participants' contextual factors, including past behaviors and individual characteristics. We will use standard moderation analysis within the GEE framework for these analyses, which involves the inclusion of main effects and interaction terms. Significant moderation effects will be probed using simple slopes analysis to determine the conditional region and direction of significance. The primary moderators to be tested are participants' 7-day history of contextual factors at the time of randomization (achievement of weight-related behavioral goals, streaks and lapses in self-monitoring, weight change, previous BCT messages received). Exploratory time-invariant potential moderators include demographic and health characteristics (e.g., sex, age, baseline BMI).

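### For active minutes, a time trend in the message effect on goal attainment cannot separate a changing message effect from a changing goal, because the goal rises with success and the time model omits it

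*Combined protocol and SAP*

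**What the plan says.** The synopsis (Study Design) gives each participant "a daily active minutes goal that gradually increases if met". Section 3 (Primary Proximal Outcome Measures) adds: "Participants will have a daily AM goal that may change or stay the same at the beginning of each program week". The primary outcome is binary against that goal: "We will calculate a dichotomous outcome of whether a participant met their daily AM goal", with days of no tracker wear counted as not met. The start value, step, trigger and any cap are not stated.

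The other two outcomes differ. Weighing has no changing goal. For red foods, "Participants will have a daily RF limit that is determined by their sex and baseline weight", and no rule for changing the limit is given.

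In section 4, the time analysis expands the primary GEE model by "including linear and quadratic main effects of time and interaction terms, between an indicator of day in the program and treatment assignment" and is to establish "the nature of the change (e.g., when effects disappear". For Aim 3, "The primary moderators to be tested are participants' 7-day history of contextual factors at the time of randomization"; the list includes recent goal achievement but not the level of the goal. The moderator method is: "We will use standard moderation analysis within the GEE framework for these analyses, which involves the inclusion of main effects and interaction terms". No link function is stated for any of these models.

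Section 3 (Secondary Outcome Measures) already includes total active minutes on the day of randomisation, which does not depend on the goal. Section 4 specifies no time or moderator model for it.

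**The concern.** Day in program is tied by design to the difficulty of the active-minutes outcome, since participants who succeed face a higher threshold later. A day-by-assignment interaction on goal attainment mixes two things: whether a message still moves behaviour as much as before, and whether the same movement still carries a participant over the line. The planned model has no term that distinguishes them.

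This matters because the plan intends to interpret the trend, including the point at which effects vanish, and because section 1 (Study Objectives) says the results will shape the optimised intervention for a later trial. Tiring of messages and goals moving away from usual activity have different design implications. The point applies to active minutes only.

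**Working it through.** **The plan's figures.** None bears directly on this point. The planned data volume reproduces: 168 × 0.83 + 84 × 0.17 = 153.72, taken as 154 days, and 201 × 154 = 30,954 person-days.

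**Why the threshold matters.** Let M be minutes without a message, with distribution function F and density f. Let the message add a constant δ minutes and let the goal be g. The effect on attainment is

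P(M + δ ≥ g) − P(M ≥ g) = F(g) − F(g − δ) ≈ δ·f(g).

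With δ constant, the effect follows the density of minutes at the goal, so it can go up or down as g rises. Two illustrations (assumed mean 35, SD 25, δ = 2):

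- Gamma (shape (35/25)² = 1.96, scale 25²/35 = 17.86): 0.0356 at a goal of 10, 0.0417 at 20, 0.0357 at 30. It rises, then falls.
- Normal: at 20, Φ(0.68) − Φ(0.60) = 0.7517 − 0.7257 = 0.0260; at 30, Φ(0.28) − Φ(0.20) = 0.6103 − 0.5793 = 0.0310. The risk difference rises. The log-odds ratio does not: ln(0.7517/0.2483) − ln(0.7257/0.2743) = 0.135 at 20, and ln(0.6103/0.3897) − ln(0.5793/0.4207) = 0.129 at 30.

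**Simulation with a goal that adapts.** All activity inputs are assumptions: mean 30 minutes a day, between-person SD 12, 10% non-wear, and daily minutes either right-skewed (gamma, shape 1.2) or normal (SD 20). The message adds 4 minutes on every day it is sent. One assignment per day has probability 0.5, over 168 days without dropout. The goal rises by 5 at the start of a week if it was met on at least the stated number of the previous 7 days.

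Large-sample message effect on goal attainment, weeks 1-4 to weeks 21-24:

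| Minutes, start goal, trigger | Risk difference | Log-odds ratio |
|---|---|---|
| Skewed, 10, 4 of 7 | 0.084 to 0.042 | 0.35 to 0.23 |
| Skewed, 20, 5 of 7 | 0.065 to 0.050 | not tabulated |
| Normal, 10, 5 of 7 | 0.047 to 0.069 | 0.22 to 0.30 |
| Normal, 30, 4 of 7 | 0.064 to 0.054 | 0.26 to 0.33 |
| Skewed, goal fixed | 0.098 to 0.097 | not tabulated |
| Normal, goal fixed | 0.039 to 0.041 | not tabulated |

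The effect fades, grows, or changes direction with the scale. With a fixed goal there is no trend, so the moving goal is the cause. A repeat of the simulation agreed to within about 0.002.

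Day-by-assignment term at N=201 (200 trials each, independence GEE, identity link, 5% test). The first two result columns give the mean coefficient and the share of trials significant; the last gives the share only.

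| Scenario | Planned model | Plus goal and goal × assignment | Total minutes as outcome |
|---|---|---|---|
| Skewed, 10, 4 of 7 | −0.048, 76.5% | −0.004, 7% | 4% |
| Skewed, 10, 5 of 7 | −0.038, 51.5% | +0.011, 6.5% | 4% |
| Skewed, 20, 5 of 7 | −0.021, 19% | −0.002, 6% | 4% |
| Normal, 10, 5 of 7 | +0.020, 20.5% | +0.018, 11% | 5.5% |
| Normal, 20, 5 of 7 | +0.005, 6.5% | +0.004, 4% | 5.5% |
| Normal, 30, 4 of 7 | −0.012, 11.5% | −0.015, 10.5% | 5.5% |
| Skewed, fixed at 10 | 0.000, 4.5% | not applicable | 4% |
| Normal, fixed at 10 | +0.001, 6.5% | not applicable | 5.5% |

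The Monte Carlo standard error at 5% is √(0.05 × 0.95/200) = 1.5 points. Total minutes holds the nominal level throughout. The linear goal terms remove the trend with skewed minutes but not in two of the three normal cases.

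**The case against.** The strongest reply is that the planned analysis is correct for what it defines. The outcome is attainment of the goal in force that day, assignment is randomised, and the contrast by day estimates the effect on that outcome without bias. If messages produce fewer met goals once goals are higher, that is a real feature of this program. Disappearance of effects is also only given as an example of what the time analysis might show, only one of three outcomes is involved, and total active minutes are already collected. All of this stands. It limits the point to interpretation, but it does not supply the missing model on total minutes.

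Three stronger readings are tempting and are not supported.

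- A reader might infer that a constant message effect will look as if it fades. The documents give neither the goal rule nor the link function, and growth or no trend is equally possible.
- A reader might compare widely separated goals and infer that most of the effect would seem lost. With the gamma above, the goal is met without a message on 27% of days at a goal of 45 and 14.5% at 60. A goal that rises only when met would seldom take such a person there.
- A reader might infer that the rising goal makes messages look weaker in recent achievers. With a rising goal, risk differences for 0-2, 3-4 and 5-7 days met were 0.052/0.055/0.059 (skewed, start 10, 4 of 7) and 0.068/0.068/0.057 (normal, start 10, 5 of 7): small and of either sign. The achievement-by-message term was significant in 5% to 14.5% of trials. With the goal fixed at 10 the pattern was stronger (skewed 0.127/0.109/0.088; significant in 54% of trials, and in 59% with normal minutes). It comes from dichotomising at a threshold, and in these cases the rising goal reduces it.

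**Conclusion.** The point holds as a limit on interpretation, for active minutes only. The documents establish that the threshold moves with success, that the outcome is binary against it, that the time model omits it, and that the trend will be interpreted. They do not establish a direction or a size. Under the assumed inputs, the planned test for change over time was significant in anything from about its nominal 5% to about three quarters of trials, although the message effect in minutes never changed.

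This rests on taking a constant effect in minutes as the meaning of an unchanged message. An effect constant on the analysis scale would show no trend. The rejection rates also assume one assignment per day, full availability and no dropout (201 × 168 = 33,768 person-days against the plan's 30,954), so they show order of size only. The primary Aim 1 contrast is not called into question. This is a cheap improvement to the Aim 2 answer, not the repair of an invalid analysis.

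**What to change.** In section 4, prespecify that for active minutes the Aim 2 time models and the Aim 3 moderator models are also run on same-day total active minutes, with goal attainment reported beside them. State that conclusions about fading or growth for active minutes will rest on agreement with the total-minutes result; where the two disagree, the trend in attainment would be described as possibly reflecting goal difficulty. For Aim 3 the reason is the dichotomisation noted above, not the rising goal.

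Add the current goal level and its product with assignment to the attainment model as a sensitivity analysis only, because a linear goal term is a partial correction. Retain the goal in force on each day in the analysis file; section 3 (Other measures) already lists goals set or modified among the data collected. State the link function for the binary models, since the direction of a trend can depend on it.

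The cost is SAP wording and some extra analysis, with no new data. The sensitivity model will have wider intervals for the time interaction because goal level and day are correlated.

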2.1 Overview and study design

The Nudge microrandomized trial (MRT) will enroll 201 young adults and test whether providing daily intervention messages tailored to recent behavior and context and targeting one of 7 different behavior change techniques (BCTs), compared with not providing a message, increases subsequent achievement of 3 daily weight-related behavioral goals (self-weighing, active minutes, red food intake). Participants will receive a mobile-delivered behavioral weight loss program and be micro-randomized three times a day over a 6-month period (i.e., 504 randomizations per individual).

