2.2 Intervention Overview

All participants will receive a 6-month core intervention adapted from the Diabetes Prevention Program specially for young adults and to be delivered remotely via an automated program. The program, Nudge, will be delivered through a native smartphone app that includes weekly lessons, weekly tailored feedback, a native food log to track red foods, visual displays of behavioral progress, and in-app messages. All participants will receive a wireless scale and an activity tracker (Fitbit, San Francisco, CA) in the mail followed by an individual videochat session with an interventionist. For each of the 24 weeks of the program, at 3 scheduled time points per day, participants will be randomized to receive or not receive a BCT message promoting achievement of proximal weight management behaviors (weighing, activity, red food intake). Thus, participants will receive 0-3 messages per day. The primary outcome is same-day achievement of daily goals (weighing, active minutes goal, red food limit), evaluated among observations in which participants received a message compared to observations in which the participant did not receive a message.

Questions answered through Nudge MRT	

 Does providing a BCT message increase goal attainment on the same day it is delivered? (Aim 1) Do each of the BCT message types have different effects on goal attainment? (Aim 1) Do BCT messages' effects change over time? If so, what is the nature of the change (i.e., when does the effect disappear)? (Aim 2) Do BCT messages work differently when delivered under different contexts (e.g., time in program, time of day, previous dose of BCT messages, recent behaviors)? (Aim 3) 	
Intervention components to be tested across 3 behaviors: 7 behavior change techniques (BCT messages)	
1.4 Action planning	Message prompts detailed planning of performance of behavior via implementation intentions
1.6 Discrepancy between current behavior and goal	Message draws attention to discrepancies between a person's current behavior and previously set outcomes goals, behavioral goals, or action plans
2.7 Feedback on outcome of behavior	Message provides feedback on the outcome of performance of the behavior (i.e., weight)
3.1 Social support	Message advises on or provides social support for performance of the behavior
6.2 Social comparison	Message draws attention to others' performance to allow comparison with person's own performance

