- *Sedentary Activity* at baseline, 3, and 6 months will be assessed with the Sedentary Behavior Questionnaire from the EARLY trials (Rosenberg et al., 2010; Lytle et al., 2014).

Psychosocial measures

- *Self-efficacy for eating*, measured using the Weight Efficacy Lifestyle Questionnaire (WEL-Q; 20 items).³⁵
- *Self-efficacy for exercise*, measured using the 12-item Self Efficacy and Exercise Habits Survey.³⁶
- *Self-regulation for exercise*, measured with the 10-item Exercise Goal-Setting Scale and the 10-item Exercise Planning and Scheduling Scale.³⁷
- *Motivation for making changes in diet* (15 items) *and exercise* (15 items), measured using the respective Treatment Self-regulation Questionnaires.³⁸
- *Perceived competence for diet* (4 items) *and exercise* (4 items).³⁹
- *Health-related quality of life*, measured using the CDC Healthy Days measure (CDC 1993).
- *Depressive symptoms*, measured using the Center for Epidemiological Studies Depression Scale (CES-D).⁴⁰

- *Weight control strategies*, measured with the Weight Control Strategies Scale (WCSS; 30 items).⁴¹
- *Hunger, restraint, disinhibition* measured using the Three Factor Eating Questionnaire (TFEQ; 51 items).⁴²
- *Perceived stress*, measured using the Perceived Stress Scale (PSS; 10 items).⁴³
- *Binge eating* measured using the revised Questionnaire on Eating and Weight Patterns (QEWP-5).⁴⁴
- *Social comparison orientation* measured using the Iowa-Netherlands Comparison Orientation Measure (INCOM; 11 items).⁴⁵
- *Weight-related information avoidance* (10 items).⁴⁶
- *Relatedness* measured with a scale adapted from Basic Need Satisfaction at Work Scale (3 items).^{47,48}
- *Message relevance* measured using 2 items from our previous work,⁴⁹ which was adapted from previous studies.^{50,51}

Other measures

We will assess several supporting measures, including sociodemographic characteristics, medical events, and medication use. Program engagement (app views, lessons accessed, feedback messages viewed, goals set or modified), process, and adherence measures (self-weighing, activity tracking, red food tracking, daily goal achievement) will be collected throughout the study period and used to calculate behavioral adherence in the prior 7 days and streaks and lapses in goal achievement. Program acceptability and satisfaction will be assessed using post-intervention program evaluation questions and in post-intervention semi-structured interviews after 6 months.

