All recruitment efforts will direct participants to a study website with a more detailed description of the research study and FAQs about participating in research. Interested individuals will click through to a REDCap web screening survey to determine initial eligibility. Those who are preliminarily eligible will be contacted by trained study staff and will undergo additional phone screening. Eligible and interested individuals will receive an email directing them to a unique REDCap link to an online informed consent. After providing consent, participants will be instructed on procedures for 1) completing one weekday and one weekend self-reported 24-hour dietary recall, 2) completing baseline online questionnaires, and 3) completing their baseline weight measurement using a Bluetooth-connected scale. The Fitbit scale and activity tracker will be mailed to the participant. After completion of baseline assessments, the participant will be scheduled for a one-on-one telephone/videochat session during which they will be informed about study procedures, assisted with downloading of the study smartphone app, and questions about getting started will be answered.

Retention

A systematic protocol will be followed to minimize dropouts. At baseline, the names and addresses of several friends and family members who can be contacted are obtained for use if we lose touch with the participant and need to contact them for study assessment completion. The study provides incentives for completing the follow-up assessments to offset any time costs and to promote retention (\$50 for completing the baseline assessment, \$25 for the abbreviated 3-month assessment, and \$75 for completing the 6-month assessment). For each assessment visit, we will send participants an email that will include a link to online questionnaires with an expected completion date as well as a scheduled date and time to step on their scale. Participants will be sent email and/or text reminders the day prior to their

telephone appointment based on their preference. Missed weights and/or calls will be immediately followed up by phone and rescheduled.

We will review participant engagement with the Nudge app weekly and will use structured protocols for promoting engagement with the intention of also promoting retention.

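### The Aim 3 moderators are 7-day histories, but randomization starts on day 1 and the moderation model does not include program day with them, so recent history can be confounded with time in program

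*Combined protocol and SAP*

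**What the plan says.** Section 4, on moderation by contextual factors, names as the primary moderators each participant's "7-day history of contextual factors at the time of randomization (achievement of weight-related behavioral goals, streaks and lapses in self-monitoring"; the list continues with weight change and BCT messages already received. The model is a GEE with the moderator's main effect and its interaction with treatment. Linear and quadratic time, and day-by-treatment interactions, are described only under the preceding Aim 2 heading. The sample size section of the same chapter says that all available observations will be used.

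Section 3, Other measures, gives the source of the histories. Engagement and adherence data "will be collected throughout the study period and used to calculate behavioral adherence in the prior 7 days and streaks and lapses in goal achievement". It has no rule for a decision point with fewer than seven prior days.

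On timing, section 2.1 says participants will "be micro-randomized three times a day over a 6-month period (i.e., 504 randomizations per individual"), and section 2.2 says "For each of the 24 weeks of the program, at 3 scheduled time points per day, participants will be randomized". Section 7 places app installation at a one-to-one session held after the baseline assessments, where the participant is "assisted with downloading of the study smartphone app". No period of goal tracking before randomization is described.

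**The concern.** A 7-day look-back needs seven days to look back on. In the first program week those days do not exist, so the history is short for every participant whatever their behavior. Aim 2 asks whether message effects change over the program. If they do, a moderator that is itself tied to program day will pick up some of the time trend unless time is in the same model.

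The possible false findings are specific: that messages work better when few have been sent recently, or that they work better after poor recent adherence, when the real cause is that messages work better early on. Section 1 (Study Objectives) says the results will shape an optimized JITAI for a later RCT and guide how messages depend on behavior and context. A false dose or adherence moderator would therefore pass directly into its messaging rules.

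**Working it through.** **1. Is there room for a run-in?** Section 2.2 gives 24 weeks and 3 decision points a day: 24 x 7 x 3 = 504, exactly the figure in section 2.1. Every one of the 168 program days has randomizations.

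**2. How much data has a short history?** Days 1-7 have 0, 1, ..., 6 prior program days, a mean of 3.
- Decision points: 7 x 3 = 21; 21/504 = 4.2%.
- The plan's person-days: 168 x .83 + 84 x .17 = 153.72, rounded to 154; 201 x 154 = 30,954, as stated.
- Week 1 person-days, with no loss in that week: 201 x 7 = 1,407; 1,407/30,954 = 4.5%.

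**3. Message count.** Assume every decision point is available and a message is sent with probability 0.5. The SAP gives 0.5 for an available message; it gives no availability figure. A full 7-day window holds 21 randomizations, with a mean of 21 x 0.5 = 10.5 messages. The chance of 4 or fewer is (1 + 21 + 210 + 1,330 + 5,985)/2^21 = 7,547/2,097,152 = 0.36%. In simulation, 86% of person-days with 4 or fewer prior messages fell in days 1-7. The low end of this moderator is thus almost entirely week 1, whatever rule is used for goal achievement.

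**4. False positives for the message count.** Simulation: 201 people, 168 days, goal rate 70%, one analyzed decision a day, no true moderation by history, 400 replicates. Effects are percentage points and are assumed; the documents give none on this scale.

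| Message effect | All days | Day 8 onward |
|---|---|---|
| Constant | 4.2% | 3.5% |
| 6 for 4 weeks, then 2 | 9.2% | 3.8% |
| 8 for 2 weeks, then 2 | 16.2% | 3.8% |
| 7 in week 1, then 2 | 14.2% | 3.5% |
| 12 in week 1, then 2 | 43.8% | 3.5% |

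Adding quadratic day-by-treatment terms, with week 1 kept, left 4.0-9.5% in the three middle rows and 25% in the last. With 17% dropout added, decaying effects gave 8-24% on all days against 3-6% from day 8 onward, and a constant effect gave 4-5%.

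**5. Goal-achievement history.** With a fixed denominator of 7, a fully adherent participant can score at most 0, .14, .29, .43, .57, .71, .86 on days 1 to 7. With available days as the denominator there is no such ceiling. Simulation with goal rates of 40% and 70%, a 2-point effect plus an assumed week-1 extra, 17% dropout and 200 replicates:

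| Week-1 extra | Fixed 7-day denominator | Available days |
|---|---|---|
| 0 points | 4.5-6% | 2-3.5% |
| 5 points | 8-10.5% | 5-6% |
| 10 points | 12.5-25.5% | 5-6% |

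**6. Dropping week 1 alone.** It removes the short windows but not later confounding. When adherence and message effects both decline over the program, two simulated settings still gave 11-21% false positives for adherence history from day 8 onward. Time has to be in the model as well.

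**The case against.** A reader might infer that first-week histories will read as low adherence. The documents do not support that. They give no denominator and no code for absent days. The rules in section 3 that score untracked days as not met define the daily outcome on study days, not days before the program. A proportion of available days fits the text equally well and gave nominal rejection rates in step 5. Nor is a message count of zero at the start a misreading: it is the true value. What remains for that moderator is its tie to program day.

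A reader might also infer that Aim 3 ignores time. It does not: the list of questions in section 2.2 names time in program as an Aim 3 context, beside previous message dose and recent behavior, and Aim 2 tests time trends directly. But nothing says that time enters the same model as each history moderator, and a separate test of time does not adjust the history interaction.

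The size is also open to challenge, and this stands. The SAP assumes a time-averaged standardized effect of .03 to .15. At a 75% goal rate (SD = sqrt(.75 x .25) = .433), 8 points is .08/.433 = .18 SD. An early effect of that size is compatible with the smaller average, but nothing in the documents predicts it. For a fixed 7-day goal count under the 8-then-2-point effect, rejection was 13.7% with flat adherence near 75%, but 5.0% both with and without week 1 when adherence fell by 30 points, because later lapses then supply most of the low histories. The simulations also use one decision a day, not three, and do not represent the sparser tests of single BCT types.

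**Conclusion.** The point holds in limited form. It follows from the documents that all first-week histories are short, that no rule covers them, and that the stated Aim 3 model does not adjust the history interaction for program day. If message effects change over the program, history moderators are then confounded with time: by construction for the message count, and for goal achievement in week 1 only under a fixed count or a not-met code. For the message count, false positives of about 8-24% rest on assumed moderate decay of the effect; sharper week-1 effects give more, and a constant effect gives no inflation. Only 4.2% of decision points have short histories, and Aims 1 and 2 are unaffected. This is a cheap improvement to the SAP, not a flaw in the trial's primary comparison.

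**What to change.** In the Aim 3 models with a history moderator:

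1. Add program day, linear and quadratic as in Aim 2, and its interaction with treatment. This is the main change, because it also deals with confounding after week 1.
2. Base the primary history analyses on decision points with seven full prior program days (day 8 onward). The quadratic time terms alone did not fully absorb a sharp week-1 effect (step 4).
3. State how each history is computed, and report a sensitivity analysis that keeps week 1 with history expressed per available prior day.

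Keep days 1-7 in Aims 1 and 2.

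The cost is SAP wording and about 4% of decision points in these models. Person-days fall from 30,954 to 30,954 - 1,407 = 29,547, and the detectable effect grows by sqrt(154/147) = 1.024, about 2.4%, before any loss of precision from the added time terms. The primary history analyses would say nothing about week 1; only the sensitivity analysis would. This departs from using every available observation, so the SAP should state the exception.
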